COMIRB Protocol

COLORADO MULTIPLE INSTITUTIONAL REVIEW BOARD
[name] [contact] [contact]

Protocol #:15-2388

Project Title: Discontinuation of Disease Modifying Therapies (DMTs) in Multiple Sclerosis (MS)

Principal Investigator: [name]

Version Date: 10Jan2020

I. Hypotheses and Specific Aims:

Main hypothesis is that relatively older MS patients with no recent signs of new inflammatory disease activity (no relapses for at least five years and no new brain MRI lesions for at least three years) while on an approved MS DMT may safely discontinue DMTs from a medical perspective, ie no greater risk of new relapses or brain MRI scan changes due to MS, compared to those staying on their DMT. Secondary hypotheses are that in individual MS patients who discontinue DMTs in this context, there will be no significant increased risk of disease progression as measured by the EDSS, and no worsening of patient quality of life as measured by a series of Patient Reported Outcomes (PROs), compared to those staying on their DMT.

Specific Aims:

In MS patients 55 years of age or older, who have no evidence of new relapses for at least five years or brain MRI lesions for at least three years while continuously taking DMTs, we will compare clinically significant and patient-relevant outcomes in those who discontinue vs continue DMTs to determine if:

1. Risk of new relapses or brain MRI lesions is no worse in those discontinuing
2. Risk of disability progression (EDSS) is no worse in those discontinuing
3. Quality of life and other patient-reported outcomes (PROs) are no worse in those discontinuing

II. Background, Preliminary Studies, and Significance:

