It is possible a patient may have asymptomatic changes on a surveillance spine MRI scan, which is not part of the protocol or SOC. Most new spine lesions will have clinical symptoms and signs associated with them, however, limiting the significance of this issue.

F. Data Analysis Plan:

- a. Aim #1: Proposed Data Analysis: We will perform a non-inferiority test for the proportions of the discontinue and continue groups experiencing a binary, protocol-defined disease event within a year. A countable event will be a new protocol-defined relapse, and/or a new brain MRI lesion. We will test the null hypothesis of inferiority with the proportion of disease events for the discontinue group being 0.08 greater (i.e., 0.10 vs 0.02) than the proportion for the continue group under the alternative that the two rates are equal. Because of the expected small numbers of events, we expect to use likelihood based exact binomial methods to obtain a confidence interval for

comparing the proportions. If the upper bound of the 95% confidence interval for the difference between the groups is less than 0.08, then we can rule out discontinuation increasing the disease event proportion by 0.08 or greater. The anticipated small number of events, and the need to use exact methods, will constrain the models that can be used in analyses. Adjustment for center heterogeneity may be attempted with Cochran-Mantel-Haenszel test, but may be similarly limited by anticipated small number of events. We will also calculate estimates and confidence intervals, using exact methods as necessary, for the proportion of disease events in both the discontinue and continue groups. In the unlikely event the proportions are relatively large, we will also calculate estimates and confidence intervals for relative risks. Larger numbers of events would permit the fitting of more complex models

b. Aim #2: Proposed Data Analysis: We will calculate estimates and confidence intervals, using exact methods as necessary, for the proportion of disease events in both the discontinue and continue groups. Aim #2 assesses progression of disability as noted on the EDSS, and this will be defined as an increase of at least one point, confirmed at 6 months, for those with a baseline EDSS ≤ 5.5 , or a change of at least 0.5 for those with EDSS of 6.0 or greater at baseline. Outcomes assessed will include % of patients with confirmed progression in each group and mean change in EDSS in each group.

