c. Aim #3: Proposed Data Analysis: Descriptive statistics on patient demographics, PDSS, MSIS, performance and NeuroQOL short form scales, and all other PROs will be prepared for treatment group by occurrence of disease event, and qualitatively compared. Pre-Post change will be compared between treatment groups. Change scores will be used for continuous and metric outcomes, and the treatment groups will be compared with two sample T-tests, or Wilcoxon tests if necessary. Binary outcomes, such as dichotomized changes in EDSS and other scales, will be tested with chi-square and proportion tests, or exact analogs if necessary. MSIS will be divided into patients with greater or less than a change of 7.5 (considered a significant change). Correlations between continuous scales will be examined, and compared between treatment groups. Events will also be compared to non-events, and combinations of (event outcome) will be tested for differences, using similar methods, in the unlikely situation there are enough events to permit meaningful statistical analysis (≥ 10 samples for an analysis group). Multiple groups can be tested with ANOVA methods for continuous outcomes, and with chi-square tests and logistic regression for binary outcomes.

Sample Size Estimation: Our null hypothesis for AIM #1, inferiority of the discontinue group, is a disease event proportion of 0.02 for the continue group, and 0.10 for the discontinue group. Our alternate hypothesis for the power calculation, non-inferiority of the discontinue group, is a disease event rate of 0.02 for both the continue and discontinue groups. Our study population consists of stable patients, so we expect the disease event rate to be very small for the continue group, and possibly the discontinue group as well. For a target alpha level of 0.025, a sample size of 112 per treatment group (225 total), would achieve 95% power for the non-inferiority test. For a single treatment group with 112 samples, if the true proportion is 0.02, then the upper bound of an exact confidence intervals can be expected to be less than 0.11 more than 95% of the time. Anticipating a dropout rate of approximately 9-15%, we plan to attempt to recruit 132 patients per treatment group (265 total).

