For secondary outcomes AIMS 2-3, a two sample t-test comparing change scores between treatment groups with an alpha level of 0.05 and an effect size equal to 38% of the standard deviation would achieve 80% power, and an effect size of 44% of the standard deviation would achieve 90% power. A two sample proportion difference test between treatment groups with an alpha level of 0.05 and an effect of approximately 0.19 would be able to achieve 80% power, and an effect of 0.22 would achieve 90% power. A relative risk test with an alpha level of 0.05, a control proportion of 0.3

or 0.5, and a ratio of 1.61 or 1.37 respectively would achieve 80% power, and a ratio of 1.71 or 1.42 respectively would achieve 90% power. A Pearson correlation of 0.27, within a group of 112 samples, between two normally distributed variables, would be detectable with 80% power for an alpha level of 0.05, and a Pearson correlation of 0.30 would be detectable with 90% power.

Table 2: Safety Comparisons of the two groups at 25 patients in each group

Sample per Group = 25		
Group	# of Events	Percent
Continue	0	0.00
Discontinue	7	28.00
Proportion		
Difference Estimate	95% Confidence Interval	
0.2800	0.1067	0.4939

Sample per Group = 25		
Group	# of Events	Percent
Continue	1	4.00
Discontinue	10	40.00
Proportion		
Difference Estimate	95% Confidence Interval	
0.3600	0.1311	0.5765

Table 3: Safety Comparisons of the two groups at 65 patients in each group

Sample per Group = 65		
Group	# of Events	Percent
Continue	1	1.54
Discontinue	15	23.08
Proportion		
Difference Estimate	95% Confidence Interval	
0.2154	0.1083	0.3407

Table 4: pValues in Dark Grey
denote statistically significant events
in discontinuers (vertical axis) vs
continuers (horizontal) at interim
analysis of 25 patients in each group.

Sample per Group = 25							
Null Hypothesis for p (Expected # of Events)							
# of Events	0.02 (0.5)	0.04 (1)	0.08 (2)	0.10 (2.5)	0.12 (3)	0.16 (4)	0.20 (5)
1	0.3965	0.6399	0.8756	0.9282	0.9598	0.9872	0.9962
2	0.0886	0.2642	0.6053	0.7288	0.8195	0.9263	0.9726
3	0.0132	0.0765	0.3232	0.4629	0.5912	0.7870	0.9018
4	0.0014	0.0165	0.1351	0.2364	0.3525	0.5837	0.7660
5	0.0001	0.0028	0.0451	0.0980	0.1734	0.3707	0.5793
6	0.0000	0.0004	0.0123	0.0334	0.0709	0.2002	0.3833
7	0.0000	0.0000	0.0028	0.0095	0.0243	0.0920	0.2200
8	0.0000	0.0000	0.0005	0.0023	0.0070	0.0361	0.1091
9	0.0000	0.0000	0.0001	0.0005	0.0017	0.0243	0.0468
10	0.0000	0.0000	0.0000	0.0001	0.0004	0.0035	0.0173

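### Aims 2 and 3 ask whether outcomes are no worse after stopping treatment, but the plan pre-specifies only per-group estimates and tests of difference, with no between-group interval or margin

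*Combined protocol and SAP*

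**What the plan says.** Section I (Specific Aims) sets the question. Aim 2: "Risk of disability progression (EDSS) is no worse in those discontinuing". Aim 3: "Quality of life and other patient-reported outcomes (PROs) are no worse in those discontinuing". The hypothesis paragraph above them words the EDSS expectation as the absence of a significant increase in risk, and the quality-of-life expectation as the absence of worsening.

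Section III.F sets the analysis.

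- **Aim 1** has a null of inferiority and a decision rule on the between-group difference: "If the upper bound of the 95% confidence interval for the difference between the groups is less than 0.08", an excess of that size is ruled out.
- **Aim 2** has estimates and intervals for the proportion progressing in each arm. "Outcomes assessed will include % of patients with confirmed progression in each group and mean change in EDSS in each group".
- **Aim 3** has descriptive statistics compared qualitatively, then tests. "Change scores will be used for continuous and metric outcomes, and the treatment groups will be compared with two sample T-tests", with Wilcoxon tests if necessary. "Binary outcomes, such as dichotomized changes in EDSS and other scales, will be tested with chi-square and proportion tests", so EDSS change also receives a test of difference here.

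The Sample Size Estimation text gives power on the same footing: "For secondary outcomes AIMS 2-3, a two sample t-test comparing change scores between treatment groups with an alpha level of 0.05", at 0.38 SD for 80% and 0.44 SD for 90%. For a difference in proportions, "an effect of approximately 0.19 would be able to achieve 80% power". It also gives power for a relative-risk test.

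**The concern.** A test of difference can detect harm, but failing to detect it does not show that harm is absent or small. An aim phrased as no worse needs either an interval for the between-group difference, so that the reader sees what worsening remains compatible with the data, or a margin against which to judge that interval. The plan does this for Aim 1 and for neither of the other two aims, although all three are worded alike.

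The wording of the secondary hypothesis makes the gap more than cosmetic, because a non-significant p-value would appear to confirm it. Section II describes acceleration of disability as part of what patients fear most about stopping, and section III.G expects the trial's progression data to guide that choice. Section III.E already warns that patient-reported outcomes may be biased because patients know their assignment. The EDSS is rated blind, so that caveat does not cover Aim 2.

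**Working it through.** **Inputs from the plan:** 112 completers per group, 1:1; alpha 0.05 for Aims 2 and 3 (sidedness not stated); the effects and powers given above. **Assumed, because the plan gives no values:** true worsenings of 0.25 and 0.30 SD; continue-group progression rates of 10%, 20% and 30%; an excess of 10 percentage points.

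**1. The plan's own power.** For a mean change, power ≈ Φ(δ√(n/2) − 1.96), with √(112/2) = 7.483.
- δ = 0.38: Φ(2.844 − 1.96) = 0.812 (0.808 by noncentral t).
- δ = 0.44: Φ(3.293 − 1.96) = 0.909 (0.906 by noncentral t).
- A difference of 0.19 in proportions near its least favourable position, 0.405 v 0.595: 0.816.
- Relative risk 1.61 at 0.3: 0.805; 1.37 at 0.5: 0.809.

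The stated figures reproduce as two-sided tests of difference. One-sided tests would give 0.883 and 0.949 for the first two. No figure is wrong; these are powers for detecting a difference.

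**2. Chance that a true worsening is non-significant, continuous outcome (t-test).**
- 0.25 SD: 1 − 0.461 = 54%.
- 0.30 SD: 1 − 0.608 = 39%.
- 0.38 SD: 1 − 0.808 = 19%.

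**3. The same for EDSS progression.** With p̄ the mean of the two rates and d their difference, power = Φ{[d − 1.96√(2p̄(1−p̄)/n)] / √([p_C(1−p_C) + p_D(1−p_D)]/n)}.
- 10% v 20%: (0.1000 − 0.0935)/0.0472 = 0.137, power 0.555, non-significant 45%.
- 20% v 30%: (0.1000 − 0.1134)/0.0575 = −0.233, power 0.408, non-significant 59%.
- 30% v 40%: (0.1000 − 0.1249)/0.0634 = −0.393, power 0.347, non-significant 65%.

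Exact binomial enumeration of the same test gives 43%, 59% and 65%. For the plan's larger effect of 0.19, the non-significant share is 5%, 12% and 17% at the same base rates.

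**4. What a 95% interval would still allow with no observed difference.**
- Mean change: 1.97 × √(2/112) = 0.263 SD.
- Risk difference, 1.96√(2p(1−p)/112): 0.079, 0.105 and 0.120 at 10%, 20% and 30%. Newcombe intervals with 11, 22 and 34 events of 112 per arm reach 0.081, 0.104 and 0.119.

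**5. Is there a usable base rate in the documents?** Section II reports 31.9% progression over a median of 4.2 years in a registry cohort that stopped treatment. Under a constant hazard, two years gives 1 − 0.681^(2/4.2) = 0.167. Aim 2 requires confirmation at 6 months and the last scheduled EDSS is at month 24, so onset must fall by about month 18: 1 − 0.681^(1.5/4.2) = 0.128. A 10-point excess is then non-significant 56% or about 50% of the time. This is illustrative only: the cohort is of stoppers over 40, not continuers aged 55 or more, and its progression was sustained for 3 months.

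**6. Smallest margin reachable with 80% power** (one-sided 0.025, true difference zero).
- Mean change: (1.96 + 0.842)√(2/112) = 0.374 SD (0.376 with the t distribution).
- Risk difference: 0.112, 0.150 and 0.172 at 10%, 20% and 30%.
- Baseline adjustment multiplies the change-score variance by (1+ρ)/2, which is 0.75 to 0.90 for an assumed baseline correlation of 0.5 to 0.8 with equal SDs. The continuous margin becomes 0.376√0.75 = 0.326 to 0.376√0.90 = 0.357 SD.

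**The case against.** The strongest reply is that these are secondary aims, the non-inferiority claim and its power rest on Aim 1, and nothing stated is numerically wrong. That is true, and it limits the weight of the point. But they are numbered specific aims, and the plan labels only the subtype and heterogeneity analyses exploratory.

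Several stronger readings are tempting, and the documents do not support them.

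- **That the plan adopts non-significance as its test of no worse.** The hypothesis wording leans that way for EDSS, but section III.F states no such rule. Nor is the document wholly silent on interpretation, since that wording is there.
- **That the information will be lost.** For EDSS progression, the risk difference and its interval can be rebuilt from the two reported proportions and group sizes. For means it can be rebuilt if SDs are reported. What is missing is a commitment to the interval as the result.
- **That no between-group measure is contemplated.** The relative-risk test in the sample-size text is one, though no interval or criterion comes with it.
- **That other text fills the gap.** The intervals for differences and relative risks in III.F belong to Aim 1. The sentence at the end of III.D that borrows the primary-outcome methods covers adverse events. The 7.5-point MSIS cut classifies individual patients and is not a between-group margin.
- **That t-tests on change scores are invalid.** They are valid in a randomised comparison. Adjusting for baseline gains precision and does not itself cure the mismatch.
- **That the registry rate measures this trial's exposure.** It does not, for the reasons in step 5 of the working.

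**Conclusion.** The concern holds in this form: the pre-specified analyses of Aims 2 and 3 can show harm but cannot support a conclusion of no worse, and the secondary hypothesis is worded so that a null result could be taken as one. With 112 per group, a 0.30 SD worsening goes undetected 39% of the time, and a 10-point excess in progression about 45% to 65% of the time. With identical observed results, worsening of about 0.26 SD or 8 to 12 percentage points remains inside the 95% interval.

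These sizes assume two-sided 0.05, full completion at 112 per group, and continue-group progression of 10% to 30%. The documents give no usable continue-group rate. Patients enrolled after July 31, 2019 may miss the month-24 visit, so fewer than 112 per group could only widen the intervals. The point should be fixed. It bears most on Aim 2, which is rated blind, and it does not touch Aim 1.

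**What to change.** 1. For confirmed EDSS progression, pre-specify the discontinue-minus-continue risk difference with its 95% interval as the reported result.
2. For mean EDSS change, continuous patient-reported outcomes and SDMT, pre-specify the between-group difference with its 95% interval, from ANCOVA with the baseline value as covariate. Keep the planned rank-based fallback for ordinal or skewed scales, reported with an interval for the shift. ANCOVA is a separate efficiency gain; a change-score difference with an interval would also close the gap.
3. Replace the secondary-hypothesis wording about no significant increase with a statement that Aims 2 and 3 are reported as estimates with intervals, and that a non-significant difference will not be read as no worse.
4. Only if a claim of no worse is wanted for a particular outcome, justify a margin and fix it before those choosing it have seen any outcome data by arm. Fixing it merely before database lock is too late, because patients and treating investigators know the assignments. Name the analysis set as well, since section III.D lets patients and physicians change treatment at any time.

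The cost is SAP wording and routine code. Baseline EDSS and patient-reported outcomes are already collected before randomisation, so no new data are needed. The downsides are slightly more analysis work and some secondary results reported as inconclusive. A claim of no worse may be out of reach for outcomes where a margin near 0.33 to 0.38 SD cannot be justified. Open-label bias in the patient-reported outcomes remains, and no interval removes it.

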This will be a randomized discontinuation trial (RDT).⁷¹ While RDTs have been done in cancer^{72,73} and rheumatoid arthritis patients,⁶⁶ this would be the first such study in MS. Patients will be randomized to either continue with their present MS DMT (control), or discontinue their present DMT (experimental), in a 1:1 fashion using the Interactive Voice Response System (IVRS) randomization system. A total of up to 265 patients will be consented and enter the trial. After allowing for up to 15% dropout rate, we aim for 225 (112 in each group) patients to complete the study. Patients enrolled after July 31, 2019 will not complete the full two years of assessments; study follow up will only continue until September 1, 2021. There will be no placebo, and no sham treatment. There will be no taper period. (Please see the statistics sections for power analyses).

At each site, extensive chart review will be used to identify eligible patients. Patients will be approached at their next standard of care clinical visit by their primary neurologist and/or a study coordinator about participating in the study. Either the patient's primary neurologist or the study PI will verify inclusion/exclusion criteria and ensure that all patient's questions are answered before consent is signed. Study information may be distributed in the community in order to recruit participants from other sources. Patients who do not receive their standard neurological care at the study site will be encouraged to transfer their neurological care to the study site for the duration of the study. If this is not possible, these subjects must agree to have standard of care MRIs done by their primary neurologist yearly throughout the study and have the results sent to the study site. MRIs at the 6-month time point must be conducted at the study site. All research visits will be conducted at the same time as SOC visits when possible, or as separate visits if not possible.

Please see Table 1 below for the schedule of study activities.

Table 1: Schedule of Research Assessments

MS Patients consented for the study	T ₀ (Baseline)	T ₁ (6 Months +/- 1 week)	T ₂ (12 Months +/- 1 week)	T ₃ (18 Months +/- 1 week)	T ₄ (24 Months +/- 1 week)***	Unscheduled Visit*	Phone follow-up (monthly +/- 1 week)
Informed Consent	X	-	-	-	-	-	
Inclusion/Exclusion	X	-	-	-	-	-	
Physical Exam/ MS Medical History	X	-	-	-	-	-	
Vitals	X	X	X	X	X	X	
Prior/Con Meds	X	X	X	X	X	X	X
Adverse Events	X	X	X	X	X	X	X

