Comorbidities	X	X	X	X	X	X	
Neuro-QoL Short Form	X	-	-	****	X	X	
PDSS	X	X	X	X	X	X	
SymptoMScreen	X	X	X	X	X	X	
MSIS-29	X	X	X	X	X	X	
SDMT	X	X	X	X	X	X	
Treatment Satisfaction Question	X	X	X	X	X	X	
Relapse Assessment	X	X	X	X	X	X	
EDSS (by unbiased Rater)	X	X	X	X	X	X	
Treatment Decision Questions	-	-	-	****	X	X	
MRI**	X	X	X	****	X	-	

*Unscheduled visits may occur for patients during the study. If an MRI is requested by the PI in relation to an unscheduled visit, that MRI would be paid through standard of care.

**T₀, T₂, and T₄ MRIs paid as part of standard of care (SOC). T₁ MRI paid as research only and must be performed at the study site. T₀ Brain MRI to be performed within 6 months preceding study entry, and will be reviewed and confirmed as fulfilling entry criteria. If T₀ MRI results for a potential subject from within the last 6 months are not available, the patient should be scheduled for a Standard of Care MRI and these results should be reviewed for inclusion/exclusion criteria prior to enrollment into the study and completion of Baseline visit.

***Participants enrolled after July 31, 2019 may not complete T₄, but will be followed until September 1, 2021. If T₃ is on or before June 30, 2021, participant should come in for an out of window T₄ visit before Sept. 1, 2021.

****If T₃ falls after June 30, 2021, participants will not come in for a T₄ visit, but will complete a NeuroQoL and Treatment Decision Question during T₃, and will have an out of window Month 24 MRI.

After thorough discussion of the trial and signing an informed consent, participants will be seen at five specified time points: T₀, screen/baseline; T₁ at 6 months; T₂ at 12 months; T₃ at 18 months; and T₄ at 24 months. Patients will be screened, have a baseline brain MRI reviewed, undergo a relapse assessment and EDSS exam, complete all PROs, and be randomized at T₀. They will be examined every 6 months at times T₀, T₁, T₂, T₃, and T₄ and undergo MRI scans of the brain at times T₀, T₁, T₂, and T₄. If T₃ occurs after June 30, 2021, participants will not be seen for a T₄ visit and they will complete the NeuroQoL and Treatment Decision Question during T₃. If the T₃ visit occurs on or before June 30, 2021, the patient will be brought back in for a T₄ visit prior to September 1, 2021. Patients who have finished the study prior to protocol v. 10Jan2020 approval will be contacted via phone to obtain verbal consent, and will then be asked the Treatment Decision Question.

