Patients will overall be randomized in a 1:1 fashion to either continue or discontinue their present DMT. They will be randomized within each site to either the continuation or discontinuation group in blocks of 2, 4 or 6 through simple random sampling. Patients with all forms of MS, RRMS, SPMS and PPMS will be offered participation, and because patients with all forms of progressive disease tend to act in a similar manner with regard to ongoing disease activity, SPMS and PPMS will be merged into a single category, progressive patients, for any subanalysis. Patients within each category, either relapsing or progressive, will also be randomized in a 1:1 fashion to continue or discontinue their DMT, but we will not stratify a certain number of either category of patients for overall participation. All MRI scans will be read locally for safety and clinical purposes, and PIs will communicate any significant MS or non-MS findings to the primary neurologist (should they not be the primary neurologist). Any new lesion documented on the T₁ or T₂ MRI scan will prompt delivery of a notice within 48 hours, to the PI, that the patient has achieved the endpoint of the study, with a description of relevant findings.

In the event of a suspected relapse, the patient will be instructed to contact their physician and the study coordinator at their local site within 48 hours of new symptoms, and come in for an unscheduled visit and relapse evaluation within seven days of symptom onset. Use of corticosteroids will be at the discretion of the patient and the local PI or other physician. Use of systemic steroids to treat MS symptoms will be concluded to be a Protocol defined relapse. As at scheduled visits, the determination of a relapse at an unscheduled visit will be made by the blinded EDSS examiner, who will perform the EDSS and only then receive information about recent clinical history.

D. Risks/Safety:

A Data Safety Monitoring Board (DSMB consisting of three board-certified neurologists not otherwise associated with the study and biostatistician) will be employed to perform twice yearly reviews of the data and certify that it is acceptable for the study to continue. It is possible that, in spite of a prolonged period with no new inflammatory disease activity, those who discontinue their DMTs will have a substantial increase in inflammatory disease activity, or progressive disease

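### Aim 3 compares change scores without adjustment; using each scale's own baseline score as a covariate is a nearly free improvement, not the repair of an error

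*Combined protocol and SAP*

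**What the plan says.** Section III.F, Aim #3, gives the comparison in two sentences: "Pre-Post change will be compared between treatment groups", and then "Change scores will be used for continuous and metric outcomes, and the treatment groups will be compared with two sample T-tests, or Wilcoxon tests". No covariate is named. For more than two groups the section names ANOVA for continuous outcomes, which again uses no baseline covariate. It names tests, not confidence intervals, for these change scores.

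The power statement for Aims 2-3, at the end of the sample-size text in III.F, rests on the same unadjusted test: "a two sample t-test comparing change scores between treatment groups with an alpha level of 0.05".

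The baseline scores exist. In III.C, patients "undergo a relapse assessment and EDSS exam, complete all PROs, and be randomized at" the T0 visit, and Table 1 lists the SDMT and every scale at T0.

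Two other places bear on adjustment:
- Section III.A, in describing the PDDS, says the instrument will serve to control for disability in both groups at all time points. No analysis section turns this into a model.
- Section III.C says: "Patients within each category, either relapsing or progressive, will also be randomized in a 1:1 fashion to continue or discontinue their DMT". The Aim 3 analysis does not use MS category, except that subgroup analyses are planned elsewhere.

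**The concern.** A change score uses the baseline in one fixed way: it subtracts it with a coefficient of 1. When the slope of follow-up on baseline differs from 1, part of the variation in the change score is still predictable from baseline, and the unadjusted test leaves that part in the error term. ANCOVA estimates the slope and removes it.

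What is at stake is the width of the intervals for the arm differences on the patient-reported scales and the SDMT. Specific Aim 3 asks whether these outcomes are no worse after discontinuation, so the amount of harm an interval can exclude matters more than a p-value. Section II also calls the patient viewpoint central to the decision being studied.

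**Working it through.** **Inputs from the document.** 112 completers per arm (Sample Size Estimation); 1:1 allocation (III.C); alpha 0.05, sidedness not stated; effects of 0.38 and 0.44 SD of the change score for 80% and 90% power (power text for Aims 2-3).

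**Inputs assumed.** The document does not give rho, the correlation of baseline with follow-up, or k, the follow-up SD divided by the baseline SD. I show rho = 0.5, 0.7, 0.8 and 0.9, with k = 1 as the main case.

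**1. The plan's own figure.** Two-sample t-test, 222 degrees of freedom, noncentrality = effect × sqrt(112/2) = effect × 7.483.
- 0.38 SD: 2.84, power 80.8% (stated 80%).
- 0.44 SD: 3.29, power 90.6% (stated 90%).

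Both reproduce with a two-sided test. A one-sided 0.05 would give about 88% and 95%, so two-sided is the reading that fits.

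**2. Gain from baseline adjustment.** With baseline SD set to 1, the change score has variance 1 + k² − 2·rho·k, and the ANCOVA residual has variance k²(1 − rho²). Their ratio is

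R = k²(1 − rho²) / (1 + k² − 2·rho·k),

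which is (1 + rho)/2 when k = 1. Interval width scales with sqrt(R).

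| rho (assumed), k = 1 | 0.5 | 0.7 | 0.8 | 0.9 |
|---|---|---|---|---|
| R | 0.75 | 0.85 | 0.90 | 0.95 |
| sqrt(R) | 0.866 | 0.922 | 0.949 | 0.975 |
| Interval narrower by | 13% | 8% | 5% | 3% |
| Power at 0.38 SD (80.8% unadjusted) | 90.5% | 86.7% | 84.7% | 82.8% |
| Unadjusted n per arm for the same precision, 112/R | 149 | 132 | 124 | 118 |

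A simulation of 4,000 trials per value at 112 per arm gave width ratios of 0.868, 0.924 and 0.977 at rho 0.5, 0.7 and 0.9, in line with the formula.

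**3. Cost of estimating the covariates.** With N = 224 and p covariates, multiply R by 1 + p/(N − 3 − p). For p = 1 the factor is 1 + 1/220 = 1.0045. For p = 2 (baseline, plus MS category assumed to explain nothing) it is 1 + 2/219 = 1.0091, so R at k = 1 becomes 0.757, 0.858, 0.908 and 0.959.

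**4. Unequal SDs.** The gain vanishes when the slope rho·k equals 1.

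| R at rho | 0.5 | 0.7 | 0.8 | 0.9 |
|---|---|---|---|---|
| k = 0.9 | 0.67 | 0.75 | 0.79 | 0.81 |
| k = 1.1 | 0.82 | 0.92 | 0.97 | 1.00 |

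The least favourable cell is k = 1.1, rho = 0.9: R = 1.21 × 0.19 / (1 + 1.21 − 1.98) = 0.2299/0.23 = 0.9996. After the cost in step 3 it is 1.004 with one covariate and 1.009 with two, a loss of 0.4% or 0.9% of variance.

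**5. Chance imbalance.** The arm difference in mean baseline has SD sqrt(2/112) = 0.134, so its 95% range is ±0.262 baseline SD. At that edge, with k = 1, the change-score contrast shifts by sqrt((1 − rho)/2) × 0.262 = 0.131, 0.101, 0.083 and 0.059 SD of change. The squared multiplier, (1 − rho)/2 = 0.25, 0.15, 0.10 and 0.05, is exactly 1 − R from step 2. The imbalance shift and the variance reduction are one quantity.

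**The case against.** The strongest reply is that this is a choice between two valid analyses of secondary outcomes. The figure that decides the gain is not in the document, and section III.E already warns that unblinded patients may bias these outcomes. In stable patients rho may be high, and the gain is then about 3% of interval width or nothing. All of that stands, and it is why this is not called an error. It does not make the choice a toss-up: over the values shown the gain in variance runs up to 33%, while the worst loss is under 1% with one or two covariates.

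Several stronger readings are tempting and are not supported:
- **That the planned test is biased or underpowered.** It is neither; its power reproduces.
- **That correcting chance imbalance is a second benefit.** Step 5 shows it is the same gain. The t-test's standard error already allows for that variation.
- **That the plan ignores covariates altogether.** The PDDS statement in III.A is an intention to control for disability. But no model carries it out, and it is not adjustment for each scale's own baseline.
- **That a site term is needed.** Randomization is by site ("They will be randomized within each site to either the continuation or discontinuation group in blocks of 2, 4 or 6"), and for Aim 1 "Adjustment for center heterogeneity may be attempted with Cochran-Mantel-Haenszel test". But the document does not give the number of sites, and fixed terms that explain nothing use up the gain.
- **That a repeated-measures model or a visit cut-off is needed.** Late entrants have shortened follow-up: "Patients enrolled after July 31, 2019 will not complete the full two years of assessments". But the share without T4 is not stated, III.E warns that dropout may depend on assignment, and nothing in the document supports a particular cut-off month.

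**Conclusion.** The point holds as a free improvement. Aim 3 leaves out a covariate that is already collected and measured before randomization. Adjusting for it would narrow the intervals by about 3 to 13% for assumed correlations of 0.9 down to 0.5 with equal SDs. If the follow-up SD is 1.1 times baseline and rho is 0.9, the gain is about zero, at a cost of 0.4% of variance with one covariate or 0.9% with two. These sizes rest on 112 completers per arm and on assumed values of rho and k.

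A reader might infer that adjustment lets Aim 3 conclude that outcomes are no worse after stopping. It does not: the document states no margin for Aim 3, so a narrower interval still has nothing to be judged against. Nor does it touch the bias from patients knowing their assignment. The gain applies to the continuous scores only.

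**What to change.** In III.F, Aim #3:
- Make the main analysis of each continuous patient-reported scale and the SDMT an ANCOVA with that scale's own T0 score as covariate. Report the adjusted arm difference with its 95% confidence interval.
- Keep the planned Wilcoxon test as a sensitivity analysis.
- Optionally add MS category (relapsing or progressive) as one further term, because allocation is 1:1 within category. Claim no precision gain for it.
- Tie the PDDS statement in III.A to this model or delete it. If it is tied in, only the baseline PDDS can be a covariate, since later values are themselves outcomes. As a third term that explains nothing it would raise the least favourable cell to 0.9996 × (1 + 3/218) = 1.013.
- Leave the 7.5-point MSIS split and the other binary analyses as planned, and leave Aim 1 unchanged.

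The cost is a few sentences and slightly more analysis work, with no new data, visits or patients. The wording should be fixed before outcomes are compared by arm.
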